6.2. Exclusion Criteria

Patients will be excluded from the study if they meet **any** of the following criteria:

- [14] are currently receiving treatment in a clinical study involving an investigational product or are enrolled into any other type of medical research judged not to be scientifically or medically compatible with this study.
- [15] have a serious concomitant systemic disorder (for example, active infection or a GI disorder causing clinically significant symptoms such as nausea, vomiting or diarrhea [such as Crohn's disease, ulcerative colitis], or profound immune suppression) or a serious preexisting medical condition (for example, history of major surgical resection involving the stomach or small bowel) that, in the opinion of the investigator, would compromise/preclude the patient's ability to adhere to the protocol.
- [16] have symptomatic central nervous system (CNS) malignancy or metastasis (screening not required).

Patients with treated CNS metastases are eligible for this study if they are not currently receiving corticosteroids (discontinued steroids at least 7 days prior to study treatment initiation) and/or anticonvulsants and their disease is asymptomatic and radiologically stable for at least 30 days.

- [17] have a symptomatic human immunodeficiency virus (HIV) infection or symptomatic activated/reactivated hepatitis A, B, or C (screening is not required).
- [18] have a personal history of any of the following conditions: syncope of cardiovascular etiology, ventricular tachycardia, ventricular fibrillation, or sudden cardiac arrest. Exceptions are:
 - patients with ablated Wolfe Parkinson White are eligible

- patients with controlled atrial fibrillation for >30 days prior to randomization are eligible.
- [19] have a history of any other cancer (except non-melanoma skin cancer or carcinoma in-situ of the cervix), unless in complete remission with no therapy for a minimum of 3 years.
- [20] had major surgery within 14 days prior to randomization to allow for post-operative healing of the surgical wound. Note: a surgery qualifies as major per investigators/surgeon judgement based on the required recovery period, both from general patient status and post-operative healing perspective.
- [21] are breastfeeding.
- [22] have received treatment with a drug that has not received regulatory approval for any indication within 14 or 21 days of the initial dose of study drug for a nonmyelosuppressive or myelosuppressive agent, respectively.

6.3. Lifestyle Restrictions

This is a lifestyle restriction study examining the relationship between timing of food and administration of abemaciclib, evaluating its impact on severe diarrhea (\geq Grade 3) or prolonged Grade 2 diarrhea (>7 days duration); see Sections 7.1 and 7.6, administration conditions and defined adherence.

Patients should avoid consumption of grapefruit or grapefruit juice while receiving abemaciclib. Patients should not donate blood during the on-study treatment period and for 3 months after discontinuing study treatment. See Section 7.7 for additional guidance on concomitant therapy to avoid whenever possible.

6.4. Screen Failures

Individuals who do not meet the criteria for participation in this study (screen failure) may be re-screened. Individuals may be re-screened up to 1 time. The interval between re-screenings should be at least 2 weeks. When re-screening is performed, the individual must sign a new informed consent form (ICF) and will be assigned a new identification number.

Repeating of laboratory tests during the screening period does not constitute re-screening.

7. Treatments

7.1. Treatments Administered

Abemaciclib monotherapy will be administered 200 mg PO BID with specific administration conditions. Patients will be instructed to take their daily doses of abemaciclib either with a meal, without a meal in a modified fasting state (defined as at least 1 hour prior to or 2 hours after a meal), or without regard to food for the first 3 cycles. Patients will be requested to record the abemaciclib dosing and administration conditions followed in a diary. Abemaciclib will be taken on Days 1 to 28 of a 28-day cycle for each treatment arm. [Table JPCP.7.1](#) shows the treatment regimens.

Patients will be instructed to commence loperamide at the first sign of loose stools and thereafter as per local label. See [Section 7.7.1.1](#) for supportive management guidance. Patients will be required to record loperamide dose and frequency in a diary. Loperamide will be supplied or reimbursed by the sponsor according to local laws. If additional antidiarrheals are prescribed by the physician, they should be entered on the concomitant medication CRF.

Table JPCP.7.1. Treatment Administration

Study Arm	Drug	Dose, mg	Route of Administration	Dose Frequency	Administration Conditions
1	Abemaciclib	200	Oral	BID	Take with a meal
2	Abemaciclib	200	Oral	BID	Take without a meal; at least 1 hour before or 2 hours after a meal (modified fasted condition)
3	Abemaciclib	200	Oral	BID	Take without regard to food

Abbreviation: BID = twice a day.

The investigator or his/her designee is responsible for the following:

- explaining the correct use of the drug and planned duration of each individual's treatment to the patient/study-site personnel/legal representative.
- verifying that instructions are followed properly the first 3 cycles. Abemaciclib is taken as per the assigned study arm outlined in [Table JPCP.7.1](#).
- maintaining accurate records of abemaciclib dispensing and collection.
- returning all unused medication to Lilly, or its designee at the end of the study, unless the site is authorized by Lilly or its designee to destroy unused medication, as allowed by local law.
- educating the patient on the management of diarrhea as per [Section 7.7.1.1](#).

7.1.1. Packaging and Labelling

Abemaciclib will be provided by Lilly and will be labeled according to the country's regulatory requirements.

7.2. Method of Treatment Assignment

Patients who meet all criteria for enrollment will be randomly assigned to 1 of the 3 treatment arms. Assignment to treatment arms will be determined by a computer-generated random sequence using an interactive Web-response system (IWRS). Randomization will be stratified by region.

7.2.1. Selection and Timing of Doses

During the on-study treatment period (primary outcome phase and extension phase), a delay of study treatment due to holiday, weekend, inclement weather, or other unforeseen circumstances will be permitted for a maximum of 7 consecutive days and not counted as a protocol deviation. In exceptional cases, for planned delays (including, but not limited to vacation or holidays), additional study treatment may be dispensed. In these cases, patients should return to the original visit schedule calculated from Day 1.

For each study arm, abemaciclib will be administered orally at 200 mg BID, with at least 6 hours separating doses on a continuous schedule and as assigned by administration conditions for each study arm. Details on treatment administration are described in Section 7.1. Treatment with abemaciclib will be given until evidence of disease recurrence or other discontinuation criteria are met (see Section 8).

7.3. Blinding

This is an open-label study.

7.4. Dose Modification

7.4.1. Special Treatment Considerations of Adverse Events of Special Interest

Table JPCP.7.2 presents dose adjustments to occur IF the event was related to abemaciclib. Any questions related to **dose adjustments** may be discussed with Lilly CRP.

Table JPCP.7.2. Dose Adjustments for Treatment-Emergent, Related*, and Clinically Significant Adverse Events of Abemaciclib

Toxicity Type	Toxicity Profile and Severity	Dose Suspension	Dose Reduction
Hematologic Toxicity	Grade 3	Dose MUST be suspended until toxicity resolves to at least Grade 2.	Dose reduction is NOT required.
Hematologic Toxicity	Recurrent ^a Grade 3	Dose MUST be suspended until toxicity resolves to at least Grade 2.	Dose MUST be reduced by 1 dose level.
Hematologic Toxicity	Grade 4	Dose MUST be suspended until toxicity resolves to at least Grade 2.	Dose MUST be reduced by 1 dose level.
Hematologic Toxicity: If patient requires administration of blood cell growth factors	Regardless of severity (Use of growth factors according to ASCO Guidelines)	Dose MUST be suspended for at least 48 hours after the last dose of blood cell growth factors was administered and until toxicity resolves to at least Grade 2.	Dose MUST be reduced by 1 dose level unless already performed for incidence of toxicity that led to the use of growth factor.
Non-Hematologic Toxicity ^b (except diarrhea, ALT increased, and ILD/pneumonitis)	Persistent or recurrent Grade 2 that does not resolve with maximal supportive measures within 7 days to baseline or Grade 1.	Dose MUST be suspended until toxicity resolves to either baseline or Grade 1.	Dose MUST be reduced by 1 dose level.
Non-Hematologic Toxicity ^b (except diarrhea, ALT increased, and ILD/pneumonitis)	Grade 3 and 4	Dose MUST be suspended until toxicity resolves to either baseline or Grade 1.	Dose MUST be reduced by 1 dose level.
Diarrhea	Grade 2 that does not resolve within 24 hours to at least Grade 1	Dose MUST be suspended until toxicity resolves to at least Grade 1.	Dose reduction is NOT required.
Diarrhea	Persistent or recurrent Grade 2 that does not resolve with maximal supportive measures, or any Grade of diarrhea that requires hospitalization	Dose MUST be suspended until toxicity resolves to at least Grade 1.	Dose MUST be reduced by 1 dose level.
Diarrhea	Grade 3 or 4	Dose MUST be suspended until toxicity resolves to at least Grade 1.	Dose MUST be reduced by 1 dose level.
ALT Increased ^c	Persistent or recurrent ^a Grade 2 (>3.0-5.0×ULN), or Grade 3 (>5.0-20.0×ULN) ^c	Dose MUST be suspended until toxicity resolves to baseline or Grade 1.	Dose MUST be reduced by 1 dose level.

ALT Increased ^c	Grade 4 (>20.0×ULN)	Abemaciclib therapy MUST be discontinued.	Abemaciclib therapy MUST be discontinued.
ALT Increased ^c with increased total bilirubin, in the absence of cholestasis	Grade 3 increased ALT (>5.0 x ULN) with total bilirubin >2 x ULN	Abemaciclib therapy MUST be discontinued	Abemaciclib therapy MUST be discontinued
ILD/Pneumonitis ^b	Grade 2 that persists or recurs despite maximal supportive measures and does not return to baseline or Grade 1 within 7 days	Dose MUST be suspended until toxicity resolves to baseline or Grade ≤1	Dose MUST be reduced by 1 dose level.
ILD/Pneumonitis ^b	Grade 3 or 4	Abemaciclib therapy MUST be discontinued	Abemaciclib therapy MUST be discontinued

Abbreviation: ALT = alanine aminotransferase; ASCO = American Society of Clinical Oncology; ILD = interstitial lung disease.

Note: MUST = mandatory.

* Related means there is a reasonable causal relationship with abemaciclib.

a Determination of persistent events will be at the discretion of the investigator. Recurrent toxicity refers to the same event occurring within the next 8 weeks (as measured from the stop date of the first event. As a general guidance, based on the risk/benefit balance assessment per the investigator, for a patient who experiences a new episode of Grade 3 hematological toxicity after more than 8 weeks following the last episode of same Grade 3 hematological toxicity, the investigator may consider resuming the patient on the same drug dose should the patient satisfy the following conditions:

- The patient showed stable hematological counts (Grade ≤2) during that timeframe
- In the absence of any infectious sign or risk factor
- The patient is benefiting from study treatment.

b Additional guidance for hepatic monitoring, renal, and ILD/pneumonitis is provided in Sections 9.4.2.1, 9.4.2.2, and 9.4.2.4.

c Grade 3 ALT increased is a trigger for additional assessments and possibly hepatic monitoring. See Section 9.4.2.1 for additional guidance for hepatic monitoring.

7.4.1.1. Dose Adjustments of Abemaciclib

Dose adjustments as outlined in Table JPCP.7.3 are allowed. Abemaciclib must be reduced sequentially by 1 dose level.

For patients requiring dose reduction(s), any re-escalation to a prior dose level is permitted only after consultation with the Lilly CRP. After re-escalation, subsequent dose adjustments should be based on the dose of abemaciclib that the patient is currently receiving.

Table JPCP.7.3. Dose Adjustments of Abemaciclib

Dose Adjustment	Oral Dose	Frequency
0	200 mg	Twice daily with at least 6 hours between doses
1	150 mg	Twice daily with at least 6 hours between doses
2	100 mg	Twice daily with at least 6 hours between doses
3	50 mg	Twice daily with at least 6 hours between doses

If a patient receiving the 50-mg BID dose of abemaciclib requires further dose reduction, the patient must be discontinued from study treatment.

7.4.1.2. Dose Delays and Omission of Abemaciclib

Suspension and delay of study treatment are permitted. When a dose suspension or delay occurs related to toxicity (defined as an AE possibly related to study treatment per investigator judgment), abemaciclib may be suspended or delayed as determined by the investigator's judgment (see [Table JPCP.7.2](#) for guidance on abemaciclib toxicity management).

Study treatment may be held up to 28 days to permit sufficient time for recovery from the toxicity.

Patients not recovering from toxicity within 28 days should be considered for discontinuation of study treatment. In exceptional circumstances, a delay >28 days is permitted upon agreement between the investigator and the Lilly CRP and abemaciclib dose adjustment is to be considered.

Patients undergoing surgery should have abemaciclib suspended. For minor surgeries and procedures (eg, ambulatory), consultation with the Lilly CRP is not required. For major surgeries, the recommendation is to suspend dosing of abemaciclib for at least 7 days before, and for up to 14 days after, the procedure. Consider monitoring neutrophils and platelets before surgery and before resuming abemaciclib. The scars should be aseptic and healing process reasonable before resuming abemaciclib. This is all monitored to prevent infection and hemorrhagic and/or healing complications. For minor surgeries, investigators should treat as clinically indicated and closely monitor any signs of infection or healing complications.

All patients who require palliative radiation should have their treatment held. This must be discussed and agreed with Lilly CRP; see Section [7.7](#).

In the event of study treatment delay due to logistical reasons (for example, due to holiday, weekend, inclement weather, or other unforeseen circumstances), the patient should continue on study treatment if the patient has adequate drug supply. If a patient's treatment is interrupted as a result of not having sufficient drug supply, study treatment may be delayed up to a maximum of 7 consecutive days (and not be considered a protocol violation). In exceptional circumstances, an additional delay up to 7 days is permitted upon agreement between the investigator and the Lilly CRP.

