7.7.1.1. Supportive Management for Diarrhea

Patients should receive instructions on the management of diarrhea and prescribed antidiarrheal therapy (protocol recommended loperamide) on Day 1. The antidiarrheal agent, loperamide is not for prophylactic use, and should only be used in the event of diarrhea. Loperamide will be supplied or reimbursed by the sponsor according to local laws. In the event of diarrhea, provided loperamide antidiarrheal therapy should be initiated as early as possible and the site should follow the guidance below:

- At the first sign of loose stools, the patient should initiate loperamide antidiarrheal therapy, if not already receiving such therapy, and notify the investigator/site for further instructions and appropriate follow-up.
- Patients should also be encouraged to drink fluids (for example, 8 to 10 glasses of clear liquids per day).
- Site personnel should assess response within 24 hours.
- If diarrhea does not resolve with loperamide therapy within 24 hours to either baseline or Grade 1, abemaciclib should be suspended until diarrhea is resolved to baseline or Grade 1.
- When abemaciclib recommences, dosing should be adjusted as outlined in [Table JPCP.7.2](#) and [Section 7.4.1.1](#).

In cases of significant diarrhea, Grades 2 through 4 ([Appendix 7](#)), that have not responded to interventions as outlined above, if the investigators are considering the addition of steroids to treat potential colitis, the sponsor strongly recommends an endoscopic procedure to document colitis prior to initiating steroids.

In cases of severe diarrhea, the measuring of neutrophil counts and body temperature and proactive management of diarrhea with antidiarrheal agents should be considered.

If diarrhea is severe (requiring intravenous [IV] rehydration) and/or associated with fever or severe neutropenia, broad-spectrum antibiotics such as fluoroquinolones must be prescribed.

Patients with severe diarrhea or any grade of diarrhea associated with severe nausea or vomiting should be carefully monitored and given IV fluid (IV hydration) and electrolyte replacement.

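### Section 7.7.1.1 puts no grade limit on its 24-hour loperamide step, while Table JPCP.7.2 requires an immediate hold and a reduction for Grade 3/4 diarrhea

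*Protocol*

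**What the plan says.** **Table JPCP.7.2 (Protocol 7.4.1)** covers events related to abemaciclib. Every diarrhea row carries the same hold: "Dose MUST be suspended until toxicity resolves to at least Grade 1". The only row with a clock is "Grade 2 that does not resolve within 24 hours to at least Grade 1", and it needs no reduction. The row for persistent or recurrent Grade 2 and for hospital admission at any grade, and the row for Grade 3 or 4, add a mandatory one-level reduction and have no 24-hour condition. The table's footnote reads "Note: MUST = mandatory".

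**Section 7.7.1.1** says that, when diarrhea occurs, "the site should follow the guidance below": start loperamide at the first loose stools and notify the site, drink fluids, and have site staff assess the response within 24 hours. Then: "If diarrhea does not resolve with loperamide therapy within 24 hours to either baseline or Grade 1, abemaciclib should be suspended". No grade is named. Dosing on restart is referred to Table JPCP.7.2 and Section 7.4.1.1. The next paragraph concerns Grade 2 to 4 diarrhea that has failed the preceding measures. The advice on severe diarrhea opens with "In cases of severe diarrhea, the measuring of neutrophil counts and body temperature" and goes on to antidiarrheals, antibiotics and intravenous fluids. It mentions neither a hold nor a reduction.

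**Section 7.4.1.2** opens with "Suspension and delay of study treatment are permitted". It then says that for toxicity "abemaciclib may be suspended or delayed as determined by the" investigator's judgment, and the same sentence refers the reader to Table JPCP.7.2.

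**Section 7.1** makes the investigator responsible for teaching patients diarrhea management from Section 7.7.1.1. The Synopsis states that treatment is outpatient.

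**The concern.** A patient with Grade 3 diarrhea should stop the drug at once and restart one level lower. Section 7.7.1.1, read alone, gives a different sequence: loperamide first, a check within 24 hours, and a hold only if the diarrhea has not come down. The section is written for the moment an episode begins, and it is the one from which outpatients are instructed, so it may well be read without the table beside it.

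What is at stake is mainly patient safety: continued dosing during a Grade 3/4 episode, or a return to full dose afterwards. A lesser matter is consistency. Interruptions and reductions due to diarrhea are endpoints under the primary objective and feed a combined endpoint in SAP 5.8, so sites should apply one rule.

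**Working it through.** **1. The rules by grade (related diarrhea)**

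| Episode | Table JPCP.7.2 | Section 7.7.1.1 alone |
|---|---|---|
| Grade 1 | no rule unless admitted | step already satisfied, no hold |
| Grade 2, first episode | hold if not down to Grade 1 at 24 h; no reduction | hold if not down to baseline or Grade 1 at 24 h |
| Grade 3/4 | hold and reduce, no wait | hold only if not down to baseline or Grade 1 at 24 h |
| Any grade, admitted | hold and reduce, no wait | no separate hold rule |

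The two texts agree in substance for a first Grade 2 episode. They differ for Grade 3/4 and for admission. The 24-hour step cannot be read as silently confined to Grade 2, because the paragraph after it applies the preceding measures to Grades 2 through 4.

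**2. A Grade 3 episode followed through**

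- Held at once: the table is met and nothing in 7.7.1.1 or 7.4.1.2 is breached.
- Managed from 7.7.1.1 alone, unresolved at 24 hours: held late. The restart pointer leads to the table, so the reduction is made.
- Managed from 7.7.1.1 alone, settled within 24 hours: no hold, so no restart, and the pointer to the reduction is never reached. The table still required both.

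**3. Dose exposure.** At 200 mg twice daily (Section 7.2.1), 24 hours is 2 scheduled doses: 2 × 200 = 400 mg at most.

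**4. Patients in whom the question arises.** Table JPCP.3.1 gives a Grade 3 rate of 20% and a Grade 4 rate of 0% in MONARCH 1. So 0.20 × 20 = 4 per arm and 0.20 × 60 = 12 in all; the 20% is not limited to three cycles. Only the share f managed from 7.7.1.1 instead of the table is exposed. The documents do not give f. As pure assumptions, f = 5%, 10% and 25% give 12f = 0.6, 1.2 and 3.0 patients; the range is 0 (f = 0) to 12 (f = 1).

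**5. Effect on the endpoints.** Interruption and reduction counts change only when the episode settles within one day. Section 3.1 gives median Grade 3 durations of 4.5, 6 and 8 days. With exponential durations (an assumption), P(T ≤ 1) = 1 − 2^(−1/m):

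- m = 4.5: 0.1428, × 4 = 0.57 per arm
- m = 6: 0.1091, × 4 = 0.44 per arm
- m = 8: 0.0830, × 4 = 0.33 per arm

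A Weibull with shape 1.5 and median 4.5 gives 1 − 2^(−(1/4.5)^1.5) = 0.0700, × 4 = 0.28 per arm.

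These values assume f = 1, that is, every site sets the mandatory row aside. They amount to 0.28/20 = 1.4 to 0.57/20 = 2.9 percentage points. At f = 25% they fall to 0.07 to 0.14 patients per arm. They are illustrations, not strict bounds: a shape below 1 would raise them, and the MONARCH durations already reflect dose adjustments.

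**The case against.** The strongest reply is that the protocol already settles the matter. The table is marked mandatory, its reduction is triggered by grade and not by whether a hold occurred, and an immediate hold is compatible with starting loperamide. Section 7.7.1.1 never says to keep dosing through Grade 3/4; its 24 hours is an outer limit on checking response. The patient must notify the site at the first loose stools, the investigator grades the episode from the e-diary and in consultation with the patient (9.4.2.5), and staff see diary data in near real time and can recommend dose changes (9.1.1). Harm requires someone to overlook a mandatory row.

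Most of this stands. It rules out the stronger reading that a reader might infer, namely that three sections contradict one another and nothing indicates which applies. It also rules out reading 7.4.1.2 as turning the table into a matter of discretion. That section is a general permission for toxicity holds, including events with no row in the table, and its own sentence sends the reader to the table. Calling the table guidance is the protocol's habit elsewhere too (9.4.2.2, 9.4.2.4).

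What does not fall away is the wording of 7.7.1.1. The safeguards make a delayed hold less likely, but they do not correct an instruction that is broader than the table allows.

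**Conclusion.** The point holds as a minor patient-safety improvement. The 24-hour step in 7.7.1.1 is over-broad for Grade 3/4 diarrhea and for diarrhea requiring admission; it does not cancel the table.

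The consequence for an affected patient is a hold late by up to two scheduled doses, or a missed one-level reduction if the episode settles first. How many patients would be affected cannot be estimated, because the share managed from 7.7.1.1 alone is unknown and would be zero if every site follows the table.

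The effect on the dose-interruption and dose-reduction endpoints is negligible: well under one patient per arm in the scenarios shown even at f = 1, and about a tenth of a patient at f = 25%. A reader might infer that the arms would be compared unfairly. The documents do not support that: the wording is the same in all three arms, the analysis is descriptive with no hypothesis tests planned (Protocol 10.3), and the episode still counts in the severe-diarrhea endpoint.

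**What to change.** In Section 7.7.1.1:

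- limit the 24-hour loperamide step to Grade 2 or lower;
- add that Grade 3/4 diarrhea, or diarrhea of any grade requiring hospital admission, is held immediately and reduced one level as in Table JPCP.7.2.

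Use the same wording in the patient diarrhea instructions. A sentence in 7.4.1.2 saying that the table governs where it has a rule would be optional clarification.

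The cost is a short protocol edit and a matching line for patients, with no new data, visits or analyses.
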